1.2 Secondary

The secondary objectives of this study are to:

- Evaluate the pharmacokinetics (PK) of AMG 596 in serum when administered by cIV infusion either in monotherapy or in combination with AMG 404
- Evaluate the pharmacokinetics (PK) of AMG 404 in serum when administered by short term infusion in combination with AMG 596
- Evaluate the clinical benefit of AMG 596 monotherapy or AMG 596 in combination with AMG 404 as determined by objective response rate (ORR) per modified Response Assessment in Neuro-Oncology Criteria (RANO) ([Okada et al., 2015](#)) in subjects with EGFRvIII-positive glioblastoma or malignant glioma in the recurrent and in the maintenance setting
- Evaluate progression free survival rate at 6 and 12 months after initiation of treatment for any Part, Arm and Group of the study

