5.1 Treatment Assignment

An Amgen representative will notify the site(s) in writing when a cohort is open to screen new subjects. This study will enroll 2 groups of subjects according to disease stage, recurrent disease (Group 1) and maintenance treatment after SoC in newly diagnosed disease (Group 2). Subjects will be treated either with AMG 596 monotherapy or with AMG 596 in combination with AMG 404 in the respective treatment arm according their individual eligibility and availability of treatment slots. If AMG 596 doses are different, mono- and combination therapy cohorts can run in parallel. If same AMG 596 doses will be explored in monotherapy and in combination, the monotherapy cohort must be completed before enrollment in the combination cohort.

Enrollment of Group 2 subjects can start after observation of a first objective response during Group 1 dose escalation.

At completion of the dose escalation cohorts, additional subjects (up to 15 Group 1 and up to 25 Group 2 subjects) will be enrolled in dose expansion cohorts to gain further clinical experience, safety and efficacy data in subjects with AMG 596 or AMG 596 in combination with AMG 404. The dose to be evaluated will be at or below the MTD estimated in the dose escalation cohorts.

Approved

The Sponsor will provide the exact treatment assignment (cohort) to sites including AMG 596 or AMG 596 and AMG 404 doses and schedule. The treatment assignment date is to be documented in the subject's medical record and on the enrollment eCRF.

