Dose escalation will be completed when any of the following occurs:

- The maximum total sample size of N = 30 DLT evaluable subjects (including single subject cohorts) is reached
- The BLRM model recommends the same dose level at least 2 times and at least 6 subjects have been treated at the recommended RP2D/MTD dose level. If step-dosing is required, this stopping criteria applies separately to each period.
- The highest planned dose level is reached without any DLTs being observed

Dose Escalation rules for Group 2: Maintenance Treatment after SoC in Newly Diagnosed Disease

- A first cohort will start after RP2D/MTD has been established in Group 1 subjects with recurrent EGFRvIII-positive glioblastoma. The starting dose in Group 2 will be decided by the DLRT and will be the MTD of Group 1, or will be no higher than a 2-fold increase of the Group 1 RP2D if no MTD was reached and no DLT was observed at the highest dose administered in Group 1 dose escalation. Treatment may consist either of [REDACTED] dose AMG 596 cIV infusion or step-dosing as established for recurrent disease. Further treatment cycles with [REDACTED] between cIV infusions will be provided until any of the treatment discontinuation criteria applies.
- The BLRM will be used to guide dose level selection. The cohort size will be N = 4-6 subjects. The actual dose selected at each dose decision may be at or below the model's recommended dose as determined by the DLRT after considering all information.

Stopping rules for Group 2: Maintenance Treatment after SoC in Newly Diagnosed Disease

Dose escalation in Group 2 will be completed when any of the following occurs.

- The maximum sample size of N = 12 DLT evaluable subjects is reached
- At least 6 subjects have been treated at the recommended RP2D/MTD dose level
- The highest pre-specified nominal dose level is reached without any DLTs being observed.

Dose expansion for Group 1 (Recurrent disease) & for Group 2 (Maintenance Treatment after SoC in Newly Diagnosed Disease):

The purpose of dose expansion will be to further explore safety and to evaluate preliminary antitumor-activity in subjects with recurrent disease (Group 1) and in

subjects in the maintenance setting (Group 2). It is anticipated that 15 subjects will be enrolled to Group 1 and up to 25 subjects will be enrolled to Group 2.

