Time to progression is calculated as the number of days from the date of first administration of AMG 596 to the initial date of radiographic progressive disease (PD) per MRI scan (Initial date of first PD – date of first dose of AMG 596+1).

The following censoring strategies for missing assessment dates will be used for the time to progression:

If a subject's disease has not progressed , time to progression will be censored at the last date they are known to be progression-free (ie, the last evaluable radiological assessment date).

If a subject has no tumor evaluation in the study, time to progression will be censored at the date of the first administration of AMG 596.

Subjects who withdraw consent to participate in the study prior to disease progression will be censored at their last evaluable radiological assessment date.

6. Analysis Sets

For all analyses, subjects will be analyzed according to the dose and treatment they received, not the dose and treatment to which they were assigned.

Safety Analysis Set

The analysis of all endpoints, unless noted otherwise, will be conducted on the Safety Analysis Set defined as all subjects that are enrolled and receive at least one administration of AMG 596.

DLT Evaluable Analysis Set

The DLT Evaluable Analysis Set will be used to summarize incidence of dose limiting toxicity (DLT). Subjects are classified as DLT-evaluable if they have had the opportunity to complete the DLT period and:

- Subject in the [REDACTED] cycle receiving a complete first cycle with 100% of the planned doses of investigational product, or
- Subject in the [REDACTED] cycle receiving at least 90% of the planned doses of investigational product or
- Subject that has experienced a DLT

Pharmacokinetic Analysis Set

The pharmacokinetic (PK) analysis set will contain all subjects for whom at least one PK parameter or endpoint can be adequately estimated.

Efficacy Analysis Set

All subjects that are enrolled and receive at least one administration of AMG 596 at the MTD will be included in the analysis of the secondary efficacy endpoints.

RANO Evaluable Analysis Set

All subjects that are enrolled and receive at least one administration of AMG 596 and who have at least one measurable lesion at baseline will be part of this analysis set.

7. Planned Analyses

There are 3 analyses (interim, primary and final) which are planned in the study.

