9.5 Efficacy Analyses

Unless otherwise specified, all subjects that are enrolled and receive at least one administration of AMG 596 at the MTD (the efficacy analysis set) will be included in the analysis of the secondary efficacy endpoints.

The following methods will be used with Kaplan-Meier analyses of efficacy endpoints.

- Estimation of the median and CI will use the Brookmeyer and Crowley (1982) method
- Landmark estimates (eg, 6 month PFS) will be estimated using the Kaplan-Meier curve and CI using Greenwood's formula to estimate the standard error (see [Kalbfleisch J.D. and Prentice R.L. \(1980\)](#))

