9.5.1 Analyses of Efficacy Endpoint(s)

Duration of Response:

Descriptive statistics will be provided. As appropriate, duration of response will be analyzed using the Kaplan-Meier method. Kaplan-Meier curves and estimates will be presented. Subjects without an objective response are excluded from the analyses of this endpoint. The median duration of response and other percentiles, as appropriate, and 80% CI will be presented. The percent of subjects with durable response at 6 and 12 months along with 80% CI will be presented.

Time to Response:

Descriptive statistics will be provided. As appropriate, time to response will be analyzed using the Kaplan-Meier method. Kaplan-Meier curves and estimates will be presented. The median time to response and other percentiles, as appropriate, and 80% CI will be presented.

Time to progression:

Time to progression will be analyzed using the Kaplan-Meier method. Kaplan-Meier curves and estimates will be presented. The median time to progression and other percentiles, as appropriate, and 80% CI will be presented. The percent of subjects who are progression-free at 6 and 12 months along with 80% CI will be presented.

Objective Response Rate:

Objective Response Rate will be analyzed using RANO Evaluable Analysis Set.

The number and proportion of patients with an objective response will be tabulated by AMG 596 dose received (MTD or other doses). An exact 80% confidence interval will be calculated using Clopper-Pearson method ([Clopper and Pearson, 1934](#). See [Appendix B](#) for code fragment) for the OR rate for all subjects in part 2 and those in part 1 treated at RP2D/MTD for each group.

Progression Free Survival:

Progression free survival (PFS) will be analyzed using the Kaplan-Meier method. Kaplan-Meier progression free survival curves and estimates will be presented. The median PFS and other percentiles, as appropriate, and 80% CI will be presented. The percentage of subjects alive and progression-free at 6 and 12 months along with 80% CI will be presented.

Response Criteria:

Response criteria will be analyzed using RANO Evaluable Analysis Set.

The number and percentage of subjects in each response category (CR, PR, SD and PD) will be tabulated by AMG 596 dose received (MTD or other doses).

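### The SAP's default efficacy set is limited to subjects dosed at the MTD, so PFS, TTP, duration of response and time to response can lose Part 2, or everyone, in scenarios the plan foresees

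*SAP*

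**What the plan says.** For the secondary efficacy endpoints, SAP Section 6 limits the Efficacy Analysis Set by dose: "All subjects that are enrolled and receive at least one administration of AMG 596 at the MTD will be included in the analysis". Neither the RP2D nor the highest tested dose is mentioned. Section 9.5 makes this set the default: "Unless otherwise specified, all subjects that are enrolled and receive at least one administration of AMG 596 at the MTD (the efficacy analysis set") go into those analyses.

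Section 9.5.1 then overrides the default twice. For response rate, "Objective Response Rate will be analyzed using RANO Evaluable Analysis Set", and the tabulation of CR, PR, SD and PD uses the same set. No set is named for the other endpoints. For example, "Progression free survival (PFS) will be analyzed using the Kaplan-Meier method" is followed by curves, medians and 6- and 12-month percentages, but no population. TTP, duration of response and time to response are treated the same way.

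On whether an MTD will exist, SAP Section 3.1 sets a Group 2 starting-dose rule for the case "if no MTD was reached and no DLT was observed at the highest dose administered in Group 1 dose escalation". It also lists reaching the top dose without a DLT as one way for escalation to end. On the expansion dose, protocol 5.1 states: "The dose to be evaluated will be at or below the MTD estimated in the dose escalation cohorts". Protocol 6.2.1.1 has expansion cohorts receive the MTD/RP2D or the highest dose tested in the group.

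**The concern.** The analysis set depends on a dose that the trial may never identify, or may not take into expansion. SAP Section 5 defines the MTD by toxicity-interval probabilities, while the protocol allows the RP2D to be a biologically active dose. The two can differ.

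Part 2 exists partly to look at preliminary antitumor activity. If its subjects are not dosed at the MTD, the time-to-event summaries would either be empty or describe a few Part 1 subjects at a dose not carried forward. Response rate would meanwhile be reported in the expansion population, so the two efficacy results would come from different subjects at different doses. An analyst would then have to choose a replacement population late, possibly with the data in view.

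**Working it through.** **1. Which set applies to which endpoint**

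| Endpoint (SAP 9.5.1) | Set named there | Set that applies |
|---|---|---|
| ORR | RANO Evaluable | RANO Evaluable |
| CR/PR/SD/PD categories | RANO Evaluable | RANO Evaluable |
| PFS, TTP, duration of response, time to response | none | Section 9.5 default: dosed at the MTD |

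SAP Section 6 also makes the Safety Analysis Set the default for all endpoints unless otherwise noted. Section 9.5 does note otherwise for efficacy, so the Safety set does not rescue these four endpoints.

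**2. Populations side by side**

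- SAP 9.5.1, ORR interval: all of Part 2, plus Part 1 subjects at the RP2D/MTD, by group.
- Protocol 10.5.3, response rate and 6- and 12-month progression-free proportions: the same population, introduced under the RANO Evaluable set.
- SAP 6 and 9.5, PFS, TTP, duration and time to response: subjects with at least one dose at the MTD.

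SAP Section 10 nevertheless reports no changes from the protocol's analyses.

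**3. The plan's own figures rest on the RP2D/MTD population**

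SAP Section 3.2 counts 6 + 15 = 21 subjects in Group 1 and 6 + 25 = 31 in Group 2. Its figures reproduce on those numbers:

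- Group 1, chance of seeing an event of 5% incidence: 1 − 0.95^21 = 65.9% (stated 66%).
- Group 1, at least 4 responses in 21 at a true ORR of 20%: 63.0% (stated 63%).
- Group 1, 4/21 = 19.0%, 80% exact interval 8.6% to 34.5% (stated 9% to 35%).
- Group 2, exact binomial recursion through the futility boundaries (0 of 10, 1 of 19, 2 of 26, 3 of 31): type I error 0.0497, power 0.803, stopping at 10 subjects 59.9%, expected additional subjects 15.55 − 6 = 9.55 (stated 0.05, 0.8, 60%, 9.6).

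**4. Membership under the literal wording**

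Counts are at planned maximum numbers, before any intra-subject escalation.

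| Scenario | Group 1 | Group 2 | Total | Of whom Part 2 |
|---|---|---|---|---|
| Expansion at the MTD | 21 | 31 | 52 | 40 |
| MTD exists, all Part 2 dosing below it | 6* | 6* | 12* | 0 |
| No MTD reached | 0 | 0 | 0 | 0 |

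*Assumes that six Part 1 subjects per group were dosed at the MTD; the plan's minimum of six applies to the recommended dose.

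Part 2 makes up 15/21 = 71% of the Group 1 population, 25/31 = 81% of Group 2 and 40/52 = 77% overall.

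**5. What the loss does to precision (illustration)**

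The 80% Clopper-Pearson limits are the 0.10 quantile of Beta(x, n − x + 1) and the 0.90 quantile of Beta(x + 1, n − x). For a progression-free proportion near one half, without censoring:

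- 3/6: 0.201 to 0.799, width 0.60
- 10/21: 0.321 to 0.636, width 0.32
- 16/31: 0.387 to 0.643, width 0.26

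**6. Can the chance of these scenarios be derived?**

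No. The chance of no DLT among the SAP's maximum of 30 Group 1 escalation subjects is (1 − q)^30 for a constant DLT rate q. The rate is an assumption that the documents do not supply: q = 1% gives 74%, 2% gives 55%, 5% gives 21% and 10% gives 4%. The range is too wide to support any statement of likelihood.

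**The case against.** The strongest reply is that this is loose drafting. The SAP usually writes RP2D/MTD as one term, so MTD here may be shorthand. If expansion runs at the MTD, the set includes Part 2 as it should. The MTD is also model-based: in Group 2 the dose-toxicity model needs no first DLT, and SAP 7.1 has it re-estimate the RP2D/MTD during expansion, so a dose might be named even without DLTs. This lowers the chance of an empty set but does not remove it. In Group 1 the model starts only after a first DLT, and the SAP itself provides for no MTD being reached. Shorthand is also a weak defence when the ORR paragraph of the same section spells out RP2D/MTD and all of Part 2.

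Several stronger readings are tempting, and the documents do not support them:

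- *No Part 2 subject can enter.* Membership needs only one dose at the MTD. Intra-subject escalation and revision of the expansion dose are both allowed, so zero of 40 is the worst case.
- *Only ORR escapes.* The response categories do too.
- *The scenario is likely.* Protocol 2.5.3.1 expects limited systemic adverse events from the drug's mechanism, not an absence of DLTs. Neurologic DLTs are defined, and the prior is set to give a DLT rate of 0.25 at the reference dose.
- *The set fails the current PFS objective.* Protocol 1.2 reads: "Evaluate progression free survival rate at 6 and 12 months after initiation of treatment for any Part, Arm and Group of the study". The reference to parts, arms and groups came with Amendment 5 (29 July 2019), after the SAP (20 May 2019). The SAP has no arms, so its 40 is the whole of Part 2. That mismatch is a matter of updating the SAP. The RP2D/MTD population for response, however, predates Amendment 5, as the amendment's own replaced text shows.
- *The data are lost.* Protocol 10.5.3 still lists TTP, time to response and duration for all subjects. Listings do not replace the planned summaries.

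**Conclusion.** The point holds as a defect of wording. Followed literally, the MTD-only default leaves PFS, TTP, duration of response and time to response with no subjects if no MTD is reached. If all expansion dosing stays below the MTD, it leaves them with none of the up to 40 Part 2 subjects, apart from any who reach the MTD by escalation or dose revision. Either outcome departs from protocol 10.5.3 and from the population the SAP uses for its own ORR interval.

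This rests on reading MTD as SAP Section 5 defines it and on Section 9.5 governing endpoints that name no other set. The counts use the planned maximum numbers.

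A reader might infer that the fault threatens the trial's main conclusions. It does not. The affected endpoints are secondary and descriptive, with 80% intervals and no test, and the primary safety analyses and the ORR futility rule do not use this set. It should be fixed, but it is not critical.

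**What to change.** In SAP Sections 6 and 9.5, replace the restriction to the MTD with the population already used for the ORR interval: every Part 2 subject, plus Part 1 subjects treated at the RP2D/MTD of their group, or at the highest tested dose if no MTD is reached. State in 9.5.1 that PFS, TTP, duration of response and time to response use it.

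Reconcile one further point with protocol 10.5.3. Its progression-free proportions follow on from a sentence limited to the RANO Evaluable set, so they can be read as restricted to measurable disease, although the eligibility criteria admit some subjects without it. The sponsor should say whether that restriction applies to the progression-free proportions and use the same answer in both documents.

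The cost is SAP wording only. No dose decision, sample size or data collection changes. It should be settled before the efficacy data are analysed.

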7.1 Interim Analysis and Early Stopping Guidelines

Part 1 Dose Escalation:

The DLRT will review the safety data after each cohort and make a decision on the next dose level to be explored for the estimate of RP2D/MTD based on a BLRM design. The RP2D/MTD will be established separately for Group 1 (recurrent disease) and Group 2

(maintenance setting) subjects. The interim analysis will include the establishment of RP2D/MTD and the estimate of ORR.

- The first interim of safety data analysis in Part 1 dose escalation will happen at the earlier of
 - When 15 subjects enrolled and completed DLT observation or
 - Completion of dose escalation of Group 1. Efficacy data will also be analyzed for subjects who have had at least one imaging evaluation after start of treatment or have dropped out before that.

Part 2 Dose Expansion:

Interim safety analyses during dose expansion will occur once 1) 5 subjects with recurrent disease have been enrolled and 2) after enrollment of 10 subjects with maintenance setting. The BLRM will estimate the RP2D/MTD using available data from dose escalation and dose expansion. Based on this revised RP2D/MTD estimate and reviewing all available safety data, the dose level for dose expansion may be revised.

In Part 2 dose expansion, the ORR will be evaluated after treating n = 10 Group 2 subjects for at least 6 months. The futility will be assessed initially for N = 10 and continuously afterwards using a Bayesian predictive probability design. Enrollment may be terminated if insufficient antitumor-activity is observed.

For stopping rules, please refer [section 3.1](#) Study Design in the SAP.

7.2 Primary Analysis

The primary analysis will occur when target enrollment in Part 1 and Part 2 is complete and each subject either completes 6 months on study or withdraws from the study.

7.3 Final Analysis

A final analysis for each group is planned after all subjects in each group have ended the study (parts 1 and 2).

8. Data Screening and Acceptance

8.1 General Principles

The objective of the data screening is to assess the quantity, quality, and statistical characteristics of the data relative to the requirements of the planned analyses.

8.2 Data Handling and Electronic Transfer of Data

The Amgen Global Study Operations-Data Management (GSO-DM) department will provide all data to be used in the planned analyses. This study will use the Rave database.

8.3 Handling of Missing and Incomplete Data

The following imputation of missing values will be done:

- Incomplete adverse event and concomitant medication dates will be imputed as per [Appendix A](#). If imputed dates are used, then they will be identified as such in the final study report.
- Non-pharmacokinetic measurements that are below the quantification limits will be considered equal to the lower limit of quantification for all analyses unless explicitly noted otherwise.

8.4 Detection of Bias

Lack of protocol compliance and the potential for biased statistical analyses will be examined by listing important protocol violations by cohort and site.

8.5 Outliers

Pharmacokinetic (PK) concentration data will be evaluated for outliers by visual inspection, and decisions to re-assay individual samples will be made in accordance with standard pharmacokinetic evaluation practice.

8.6 Distributional Characteristics

Where appropriate, the assumptions underlying the proposed statistical methodologies will be assessed. If required data transformations or alternative non-parametric methods of analyses will be utilized.

8.7 Validation of Statistical Analyses

Programs will be developed and maintained, and output will be verified in accordance with current risk-based quality control procedures.

Tables, figures, and listings will be produced with validated standard macro programs where standard macros can produce the specified outputs.

The production environment for statistical analyses consists of Amgen-supported versions of statistical analysis software; for example, the SAS System version [9.3] or later.

9. Statistical Methods of Analysis

9.1 General Considerations

Descriptive statistics will be provided for selected demographics, safety, PK, PD, efficacy data by dose, dose schedule, and time as appropriate.

Descriptive statistics on continuous data will include means, medians, standard deviations and ranges, while categorical data will be summarized using frequency counts and percentages.

ORR will be presented with 80% Clopper-Pearson exact CI. PFS will be summarized using Kaplan-Meier method. Graphical summaries of the data may also be presented, eg. duration on study, changes in tumor load per time.

